1. SYNOPSIS

PROTOCOL: Clinical Investigation of the Safety and Effectiveness of an Investigational Model of the TECNIS® Intraocular Lens

Protocol Number: SUR-CAT-652-2001

STUDY TREATMENTS:

Investigational Lens:

TECNIS IOL Model ZFR00V (presbyopia-correcting IOL made with OptiBlue material, which contains a violet-blocking chromophore)

Control Lens:

TECNIS IOL Model ZCB00 (colorless monofocal, Johnson & Johnson Surgical Vision,), commercially available

STUDY OBJECTIVE:

The purpose of this clinical trial is to evaluate the safety and effectiveness of the investigational IOL Model ZFR00V in comparison to a monofocal IOL.

CLINICAL HYPOTHESIS:

The investigational IOL Model ZFR00V will provide improved distance-corrected near visual acuity, as well as decreased spectacle wear compared to the monofocal control TECNIS 1-piece IOL Model ZCB00. The mean best-corrected distance acuity of the investigational IOL Model ZFR00V will be non-inferior to that of the monofocal control IOL Model ZCB00.

Complication and adverse event rates associated with the investigational IOL Model ZFR00V will be within the rates for posterior chamber IOLs given in ISO 11979-7:2018.

OVERALL STUDY DESIGN:

Structure: Prospective, multicenter, bilateral, three-way masked (sponsor, subject and evaluator), randomized clinical trial

Number of sites: Up to 15 sites in the United States

Duration: 6 months postoperative follow-up

Administration: Surgeons will perform routine, small-incision, cataract surgery and implant the study lenses using a

sponsor-recommended implantation system. Refractive target outcomes will be emmetropia for both eyes.

Visit Schedule: Subjects will be randomized to a treatment group (masked) and bilaterally implanted with the same lens type; the second eye is to be implanted within 1 month of the first eye surgery.

All subjects will undergo 9 scheduled visits: Preoperative for both eyes; Operative, 1-day, and 1-week visits for each eye; and 1-month and 6-month visits for both eyes.

STUDY POPULATION CHARACTERISTICS:

Condition: Bilateral cataracts with otherwise-healthy eyes

Number of Subjects: Up to 300 subjects (150 per lens group) will be enrolled, allowing for 10% screening failures, to achieve approximately 135 bilaterally-implanted subjects in each lens group. Allowing for 10% lost to follow-up, this will achieve approximately 122 evaluable subjects at 6 months postoperative in each lens group in the study.

Each site should enroll approximately 20 subjects, and no site may enroll more than 25% of the enrollment total.

Inclusion Criteria (all criteria apply to each study eye):

- Minimum 22 years of age
- Bilateral cataracts for which posterior chamber IOL implantation has been planned
- Preoperative best-corrected distance visual acuity (BCDVA) of 20/40 Snellen or worse with a glare source or 20/40 Snellen or worse without a glare source
- Potential for postoperative BCDVA of 20/30 Snellen or better
- Corneal astigmatism:
 - Normal corneal topography
 - Predicted postoperative corneal astigmatism of less than 1.00 D in both eyes, including posterior corneal astigmatism (PCA)
- Clear intraocular media other than cataract in each eye
- Availability, willingness and sufficient cognitive awareness to comply with examination procedures and study visits
- Signed informed consent and HIPAA authorization or equivalent documentation necessary to comply with applicable privacy laws pertaining to medical treatment in the governing countries
- Ability to understand and respond to a questionnaire in English.

Exclusion Criteria (all criteria apply to each study eye):

- Requiring an intraocular lens power outside the available range of +14.0 D to +26.0 D
- Any clinically-significant pupil abnormalities (non-reactive, fixed pupils, or abnormally-shaped pupils)
- Inability to focus or fixate for prolonged periods of time (e.g., due to strabismus, nystagmus, etc.)
- Prior corneal refractive (LASIK, LASEK, RK, PRK, etc.) or intraocular surgery, including prophylactic peripheral iridotomies and peripheral laser retinal repairs
- Corneal abnormalities such as stromal, epithelial or endothelial dystrophies (e.g., any observed guttata) that are predicted to cause visual acuity losses to a level worse than 20/30 Snellen during the study
- Irregular corneal astigmatism
- Inability to achieve keratometric stability for contact lens wearers (as defined in Section 10.3 Preoperative Procedures)
- Recent ocular trauma or ocular surgery that is not resolved/stable or may affect visual outcomes or increase risk to the subject
- Subjects with diagnosed degenerative visual disorders (e.g., macular degeneration or other retinal disorders) that are predicted to cause visual acuity losses to a level worse than 20/30 Snellen during the study
- Subjects with conditions associated with increased risk of zonular rupture, including capsular or zonular abnormalities that may lead to IOL decentration or tilt, such as pseudoexfoliation, trauma, or posterior capsule defects
- Use of systemic or ocular medications that may affect vision
- Prior, current, or anticipated use during the course of the 6-month study of tamsulosin or silodosin (e.g., Flomax, Flomaxtra, Rapaflo) that may, in the opinion of the investigator, confound the outcome or increase the risk to the subject (e.g., poor dilation or a lack of adequate iris structure to perform standard cataract surgery)
- Poorly-controlled diabetes
- Acute, chronic, or uncontrolled systemic or ocular disease or illness that, in the opinion of the investigator, would increase the operative risk or confound the outcome of the study (e.g., immunocompromised, connective tissue disease, suspected glaucoma, glaucomatous changes in the fundus or visual field, ocular inflammation, etc.). Note: controlled ocular hypertension without glaucomatous changes (optic nerve cupping and visual field loss) is acceptable.
- Known ocular disease or pathology that, in the opinion of the investigator,
 - may affect visual acuity
 - may require surgical intervention during the course of the study (macular degeneration, cystoid macular edema, diabetic retinopathy, uncontrolled glaucoma, etc.)
 - may be expected to require retinal laser treatment or other surgical intervention during the course of the study (macular degeneration, cystoid macular edema, diabetic retinopathy, etc.)
- Pregnancy, planned pregnancy, presently lactating, or another condition associated with hormonal fluctuation that could lead to refractive changes
- Concurrent participation or participation within 60 days prior to preoperative visit in any other clinical trial

- Desire for monovision correction.

EVALUATION CRITERIA:

The purpose of this clinical study is to evaluate the safety and effectiveness of the investigational IOL Model ZFR00V. Clinical endpoints and success criteria for this evaluation are defined below.

EFFECTIVENESS

The primary effectiveness endpoint for the study is the mean monocular distance-corrected near visual acuity (40 cm) under photopic conditions.

The secondary effectiveness endpoints for the study are:

1. Monocular DCIVA (66 cm) under photopic conditions
2. Monocular DCNVA (33 cm) under photopic conditions
3. Monocular BCDVA under photopic conditions
4. Monocular distance-corrected defocus curve
5. Spectacle wear

SAFETY

Primary Safety:

1. The rate of secondary surgical interventions (SSIs) related to optical properties of the lens in first eyes of subjects in the test group
2. All SPE types of adverse events, including total SSIs, reported among first eyes of subjects in the test group will be compared to ISO SPE rates.
3. All other types of adverse events (non-SPE) will be analyzed

Co-Primary Safety:

1. The proportion of first eyes in the test group that achieves monocular BCDVA percent of 20/40 or better will be compared to the ISO SPE rate.

Secondary Safety:

The binocular and monocular (first eyes) best-corrected distance contrast sensitivity for the test group will be compared to that of the control (mesopic with and without glare at 1.5, 3, 6, and 12 cpd, photopic with glare at 3, 6, 12, and 18 cpd).

For primary and co-primary safety endpoints, additional secondary analyses consisting of second eyes and all eyes (pooling first and second eyes) will also be included.

OTHER ENDPOINTS

Other endpoints in the study include:

- Binocular distance-corrected defocus
- Monocular (first eye) and binocular mesopic DCNVA at 40 cm
- Monocular (first eye) UCDVA
- Binocular UCDVA, UCIVA, and UCNVA
- Binocular BCDVA and DCNVA at 40 cm
- Medical findings/complications
- Lens findings/complications
- Residual refractive error
- Visual symptoms reported via PRO instrument (Patient Reported Visual Symptoms Questionnaire [PRVSQ])
- Ocular/visual symptoms (non-directed responses to the open-ended question “Are you having any difficulties with your eyes or vision?”)

- Satisfaction and other questionnaire responses

DATA ANALYSIS:

The investigational IOL Model ZFR00V will be compared to the control IOL Model ZCB00. The 6-month postoperative visit is the key analysis time point for all endpoints, although data will be reviewed at other time points as well.

For the primary effectiveness endpoint (DCNVA at 40 cm) and monocular secondary effectiveness endpoints (DCIVA, DCNVA at 33 cm, and BCDVA), the primary analysis population will be a modified Intent-to-Treat (mITT) analysis for all first eyes randomized and implanted with either a test or control lens.

For the spectacle wear secondary endpoints based on binocular measurements, the primary analysis population will be a modified Intent-to-Treat (mITT) analysis that only includes subjects randomized and binocularly implanted with the same lens model (either investigational or control lenses in both eyes). Any missing values at the 6-month postoperative visit will be imputed in ITT and mITT analyses.

Since there are no inferential statistics for the monocular defocus curve secondary endpoint, a safety population (SP), with available data (i.e., no data imputation) and with subjects randomized and implanted with either an investigational or control lens will be the primary analysis population. The SP will also be used for safety endpoints and other endpoints. With the exception of spectacle wear data, binocular, second-eye and pooled eye data will be considered supplementary and will be used for secondary analyses. Per-protocol analysis will be performed for primary and secondary endpoints. Sensitivity analysis will also be performed for primary DCNVA (40 cm) endpoint and secondary DCIVA, DCNVA (33 cm), BCDVA, and spectacle wear endpoints. Please see detailed descriptions of the analysis populations in Section 20.1.

All data will be reported by IOL group.

STUDY VISITS AND PROCEDURES:

Inclusion and exclusion qualifications will be assessed at the preoperative visit according to the inclusion/exclusion criteria. The Informed Consent Form and Authorization for Use/Disclosure of Health Information form (HIPAA authorization) must be signed by any patients who agree to participate in the study prior to undergoing any study-specific procedures. Those subjects who meet the inclusion/exclusion criteria and agree to participate will be randomized to a treatment group in a masked fashion and implanted in both eyes: either the test Model ZFR00V IOL or control Model ZCB00 IOL. The eye implanted first will be considered the primary study eye. All subjects are intended to have bilateral cataract surgery with the second-eye surgery occurring after the 1-week exam for the first eye but no more than 30 days after the first eye surgery. Study subjects as well as personnel performing the postoperative vision testing and refractions

will be masked for the duration of the study. In addition, key Sponsor personnel will be masked during the study, as necessary.

Key preoperative data include ocular health and history, visual acuities, manifest refraction, keratometry, biomicroscopic slit-lamp findings, ocular symptoms, and biometry. The operative visit will include standard procedures for cataract surgery and IOL implantation. Key postoperative data include monocular and binocular uncorrected and distance-corrected visual acuities under photopic and mesopic lighting conditions, contrast sensitivity, defocus curve, slit-lamp findings, non-directed visual symptoms, questionnaires, and adverse events.

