In addition, if a subject is seen after the 1-month postoperative visit for an unscheduled visit due to an optical/visual symptom complaint, the PRVSQ will be administered at that visit, as well as prior to any secondary surgical intervention for an optical/visual symptom complaint. If additional unscheduled visits and/or a secondary surgical intervention due to the same optical/visual symptom complaint occur within 2 weeks of each other, it is not necessary to complete the PRVSQ a second time.

The optical visual symptom complaints that trigger the need for the PRVSQ to be administered at an unscheduled visit include any of the seven symptoms from the

PRVSQ: halos, glare, starbursts, sensitivity to light, occlusions, multiple or double vision or poor low light vision.

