10.8 EXIT OF SUBJECTS

An Exit CRF will be completed for each subject that completes the study or exits the study before completing all scheduled visits.

It is the responsibility of the investigator to provide complete follow-up data to JJSV for each subject, and every attempt should be made to gather that complete follow-up data for all subjects enrolled, as missing data can have a negative effect on the study results. Patients who would be traveling, relocating or otherwise unavailable for postoperative follow-up visits should not be enrolled in this clinical study.

A subject will be considered a "screen failure" if he/she does not meet the eligibility criteria, consent is withdrawn prior to randomization or surgery, implantation in the first eye is aborted due to a surgical complication, or the subject dies prior to first-eye treatment.

Subjects will be "discontinued" from the study if the subject is randomized but does not undergo surgery; or if one study lens (if implanted unilaterally) or both study lenses (if implanted bilaterally) are removed; or if the subject dies.

If a subject receives at least one study lens, he/she is to be followed according to the schedule in Table 2 (**Section 10.2**) for visit windows.

Subjects will be considered "lost-to-follow-up" from the study only if irretrievably lost for unavoidable reasons such as: subject moved/unable to locate, subject ill/unable to travel, subject uncooperative/refuses further study participation. In the event of subject relocation, effort must be made by the investigator to secure follow-up information (i.e., slit-lamp findings and general visual acuity, etc.) from the subject's new physician.

If a subject is exited early from the study, the investigator must indicate the reason for study exit on the CRF. In the event of a lens removal or other serious adverse event, the subject may be exited from the study; however, effort must be made by the investigator to follow the subject until resolution of the adverse event before exiting the subject from the study.

All study subjects are to be instructed to undergo regular eye examinations at least yearly and also to return to their doctor if any eye complications are experienced.

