20.1 ANALYSIS POPULATION

For the primary effectiveness endpoint (DCNVA at 40 cm) and monocular secondary effectiveness endpoints (DCIVA, DCNVA (at 33 cm) and BCDVA),

For eyes that do not have data available at the 6-month postoperative visit, data will be imputed for the mITT population analyses. For continuous variables (DCNVA, BCDVA and DCIVA), planned method to use is the MCMC full-data imputation as described in Little & Rubin³ .

³ Little, R. and Rubin, D. Statistical Analysis with Missing Data, John Wiley & Sons, Inc. New York, Second Edition, (2002).

⁴ SAS Institute. The MI and MIANALYZE Procedures. SAS/STAT 9.2 User Guide. and SAS/STAT User Guide for the MI Procedure: Imputation Methods. Cary, N.C.

A Per-Protocol (PP) analysis will also be used for primary effectiveness and secondary endpoints. The PP population for monocular data will include eyes with a test or control lens implanted, evaluated within the proper study interval and without clinically-relevant protocol deviations (deviations that could potentially impact the primary or secondary endpoints) as determined prior to database lock. The PP population for binocular data will include subjects that do not have any of the deviations stated above in either eye. PP tables will include available data at the time of analysis.

The safety population (SP) will consist of all eyes and subjects implanted with either a test or control IOL(s) and with data available at the time of analysis (i.e., no data imputation). Reporting of cumulative complications and adverse events (occurring at any time postoperative) will include data from all study eyes implanted. For all safety endpoints and other endpoints, only safety population will be used. For BCDVA percent 20/40 or better vs. ISO SPE rate, a best-case population will also be used, consisting of eyes in the safety population without any clinically-relevant preoperative ocular pathologies or macular degeneration detected at any time.

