2 ANALYSIS POPULATIONS

2.1 ANALYSIS POPULATIONS/HANDLING OF MISSING DATA

For the primary effectiveness endpoint (DCNVA at 40 cm) and monocular secondary effectiveness endpoints (DCIVA, DCNVA (at 33 cm), and BCDVA),

For eyes that do not have data available at the 6-month postoperative visit, data will be imputed for the mITT analyses. For continuous variables (DCNVA, BCDVA and DCIVA), the planned method to use is the MCMC full-data imputation as described in Little & Rubin².

A Per-Protocol (PP) analysis will also be presented for primary effectiveness and secondary endpoints. The PP population for monocular data will include eyes with an investigational or control lens implanted, evaluated within the proper study interval and without clinically-relevant protocol deviations (deviations that could potentially impact the primary or secondary endpoints) as determined prior to database lock. The PP population for binocular data will include subjects that do not have any of the deviations stated above in either eye. PP tables will include available data at the time of analysis (i.e., no data imputation).

The safety population for monocular variables will consist of all eyes implanted with either a test or control IOL(s) and with data available at the time of analysis (i.e., no data imputation). The safety population for binocular variables will consist of all subjects implanted with the same test or same control IOLs in both eyes and with data available at the time of analysis (i.e., no data imputation). For secondary monocular defocus curve, safety population will be used for the primary analysis since there is no inferential statistics required for that endpoint. For all safety endpoints and other endpoints, the safety population will be used. For BCDVA percent 20/40 or better vs. ISO SPE rate, a best-case population will also be used, consisting of eyes in the safety population without any clinically-relevant preoperative ocular pathologies or macular degeneration detected at any time.

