For the primary DCNVA (at 40 cm), secondary DCIVA, DCNVA (at 33 cm), BCDVA, and spectacle wear endpoints, the mITT, sensitivity, PP and safety populations will be used for data reporting. For defocus curve secondary endpoint, only safety and PP populations will be used for data reporting. For safety endpoints and other endpoints, the safety population will be used. The primary analysis will be based on first-eye data, unless stated otherwise. Some visual acuity variables will also be reported separately for second eyes as supportive data only. Safety (adverse events in both ISO SPE and non-SPE, medical findings, lens findings and non-directed ocular visual findings), monocular effectiveness endpoints (DCNVA, BCDVA, DCIVA) and monocular mesopic DCNVA will also be reported using all eyes (i.e., pooling first and second eyes by adding them together) as supporting data. Descriptive statistics will be presented for all eyes analysis. Appendix I lists the analysis tables including the endpoints and the populations used to report the results.

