6.10 VISUAL SYMPTOMS VIA PRO INSTRUMENT

Visual symptom data obtained from the PRVSQ instrument at 6-month will be reported for subjects who have received the same test lenses or same control lenses in both eyes. The frequency and proportion of subjects with a given response will be reported by IOL group.

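### The primary spectacle-wear set and the 6-month visual-symptom table require the same lens in both eyes, which is settled after the first lens has been experienced, and no visible rule covers lens-related refusal or removal.

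*Protocol*

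**What the plan says.** **Spectacle wear.** The Data Analysis part of the protocol synopsis defines the primary population as an mITT "analysis that only includes subjects randomized and binocularly implanted with the same lens model". It adds: "Any missing values at the 6-month postoperative visit will be imputed in ITT and mITT analyses". By contrast, the monocular acuity endpoints use all first eyes randomised and implanted. Protocol 6.2 (item 5) sets two clinical criteria for being spectacle-free in all four conditions: at least 50% of test subjects, and at least 25 percentage points more than control. SAP 2.1 lists further reporting sets for the acuity and "spectacle wear endpoints, the mITT, sensitivity, PP and safety populations will be used for data reporting".

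**Visual symptoms.** SAP 6.10 says that 6-month PRVSQ data "will be reported for subjects who have received the same test lenses or same control lenses in both eyes". SAP 6.11 restricts satisfaction data likewise. Protocol 10.7 also has the PRVSQ completed at unscheduled visits for a visual complaint, "as well as prior to any secondary surgical intervention for an optical/visual symptom complaint".

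**Timing and exit.** Protocol 10.1 and 10.2 place second-eye surgery after the first eye's 1-week exam and within 30 days of the first surgery. Note b to Table 2 keeps a subject without a second implant in follow-up to 6 months. Under Protocol 10.8 a subject is discontinued if the only study lens is removed, or if "both study lenses (if implanted bilaterally) are removed".

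**The concern.** Membership of the spectacle-wear set depends on an event that comes after randomisation and after at least a week with the assigned lens. Refusal of a second implant because of halos or poor vision is related to the outcome, so leaving such subjects out breaks the randomised comparison in a direction that can be anticipated. Protocol 17 says that dysphotopsias may be expected with the test lens and that the lens may be removed if necessary.

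At stake are a secondary effectiveness endpoint judged against fixed cut-offs, and the patient-reported symptom table. That table would omit the questionnaires taken from subjects about to have a lens exchanged or removed for their symptoms.

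**Working it through.** **1. The plan's own figure.** Protocol 20.7 and SAP 7.3 claim more than 90% power for 80% versus 60%, with a one-sided Fisher's exact test, alpha 0.025 and 122 per group. Enumerating both binomial distributions gives 91.4%, so the claim reproduces. The planned flow is 150 × 0.9 = 135 bilaterally implanted per group, then 135 × 0.9 = 121.5, about 122 evaluable.

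**2. What happens to each kind of subject in the visible text.**
- *Refuses the second lens because of the first:* followed to 6 months, when questionnaires are given (Protocol 10.7), but outside the spectacle-wear mITT and the PRVSQ table. The SAP safety set does not help: "The safety population for binocular variables will consist of all subjects implanted with the same test or same control IOLs in both eyes". Protocol 20.1 words the safety set more broadly.
- *Both lenses removed after bilateral implantation:* still meets the mITT definition. The subject is discontinued, and a missing 6-month answer is imputed.
- *One of two lenses removed:* not automatically discontinued under Protocol 10.8, so may give an observed answer.
- *PRVSQ before a secondary intervention:* collected, but no visible table reports it.

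The only visible imputation rule covers acuity: "For continuous variables (DCNVA, BCDVA and DCIVA), planned method to use is the MCMC full-data imputation". No rule for the binary spectacle endpoint can be seen.

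**3. Effect of leaving out refusers.** The documents give no refusal rate, so the number k is an assumption. The 135 per group are already bilaterally implanted, so refusers are added to the denominator. A test rate of x/135 becomes x/(135 + k). Control is held at 75/135 = 55.6%.

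| Test successes | k | Test rate | Difference (points) | 25-point criterion |
|---|---|---|---|---|
| 109 | 0 | 109/135 = 80.7% | 25.2 | met |
| 109 | 1 | 109/136 = 80.1% | 24.6 | missed |
| 109 | 3 | 109/138 = 79.0% | 23.4 | missed |
| 109 | 6 | 109/141 = 77.3% | 21.7 | missed |
| 112 | 0 | 112/135 = 83.0% | 27.4 | met |
| 112 | 3 | 112/138 = 81.2% | 25.6 | met |
| 112 | 6 | 112/141 = 79.4% | 23.9 | missed |

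The starting counts were chosen to lie near the cut-off. If 3 refusers occurred in each arm, the first case would be (109 − 75)/138 = 24.6 points. That is a fall of about 0.5 points, against about 1.8 when all 3 are in the test arm.

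The 50% criterion is sensitive only near 50%: 68/135 = 50.4% becomes 68/138 = 49.3%. At the planned 80% (108/135) it would take 82 added failures to fall below 50%, since 108/(135 + k) < 0.5 needs k > 81.

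**4. Effect of imputing removed subjects.** Suppose k of 135 test subjects would be imputed at the planned 80%, and score them as failures instead. The test rate becomes 0.80 × (135 − k)/135, a loss of 0.8/135 = 0.6 points each. With control at 60% and 135 per group, exact power is:
- k = 0: 93.9%
- k = 2: 90.5% (test rate 78.8%)
- k = 3: 88.3% (78.2%)
- k = 5: 83.0% (77.0%)

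If the rule that cannot be seen already scores removals as failures, this effect is nil.

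**The case against.** The strongest reply is that the plan may already deal with part of this. A spectacle-wear sensitivity analysis is promised, the synopsis mentions ITT imputation, and SAP 2.4 keeps subjects with a non-study lens or cancelled surgery in their randomised group for further analyses. The binary imputation rule, the sensitivity details and the list of tables are not in the text available. This stands as a limit on what can be claimed. It does not answer the point, because the visible SAP 2.4 rule names neither lens-related second-eye refusal nor later removal, and the primary set is stated plainly.

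Safety is also covered elsewhere. Optical secondary interventions in first eyes are a primary safety endpoint (Protocol 6.3), and non-directed symptoms are tabulated by eye without the bilateral restriction (SAP 6.9). That too stands, although a safety count does not correct an effectiveness proportion. The PRVSQ is listed among other endpoints (Protocol 6.4), so it should not be called the main safety table.

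A reader might subtract refusers from the 135, turning 107/135 (79.3%, 23.7 points above control) into 107/132 (81.1%, 25.5 points). The documents do not support this, because the 135 already excludes refusers. Adding 3 gives 107/138 = 77.5% and 22.0 points, so the criterion is missed either way.

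Finally, scoring every subject without bilateral study lenses as a failure would sweep in second-eye surgical complications (Protocol 10.6) and unrelated cancellations. That objection is fair and limits the fix.

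**Conclusion.** The point holds for the visible primary spectacle-wear analysis and the PRVSQ table. Lens-related refusers are excluded after randomisation, removed bilateral subjects are retained with missing answers imputed, and no visible rule treats either event as an outcome.

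A reader might infer that these subjects are definitely not scored as failures, or that no other analysis includes them. Neither can be confirmed, because the relevant rules are not visible. Nor does Protocol 17 predict refusals or removals; it expects dysphotopsia and allows removal.

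The size depends on unknown counts. With 135 bilaterally implanted per group and a test rate near 80%, one to six test-arm refusers counted as failures lower the difference by about 0.6 to 3.4 points, assuming no refusers in control. That can decide the 25-point criterion when the result is close to it. It is very unlikely to decide the 50% criterion at the planned rate. The sample-size statement is not in error.

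**What to change.** In the SAP:
1. Make the primary spectacle-wear set all subjects randomised and implanted in the first eye, by randomised lens, as for the monocular endpoints.
2. Count as not spectacle-free a subject who declined the second study lens for a lens-related reason, or who had a study lens removed for optical or visual reasons.
3. Handle unrelated causes, such as a second-eye surgical complication or an unrelated cancellation, by the plan's missing-data method, and state that method for the binary endpoint.
4. Keep the bilateral set as supportive.
5. Tabulate, by randomised lens, the pre-intervention PRVSQ of subjects who had a secondary intervention, beside the 6-month table.

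The cost is SAP wording and one more table, using questionnaires already scheduled. The visible text asks for a reason only at early exit (Protocol 10.8), so the sponsor should confirm that the reason for a missing second implant is also recorded when the subject stays in follow-up. The spectacle-free rate may be slightly less favourable.
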